# 3. STUDY DESIGN

# 3.1. General Description

This is a phase II, single-blind, randomized, controlled, multi-country study in healthy children of 4 to 6 years of age. Participants will be randomized to a single dose of MMRVNS vaccine (3 groups of 200 participants each receiving one of the 3 different vaccine formulations [MMRV(H)NS vaccine, MM(H)RVNS vaccine and M(L)M(L)R(L)V(L)NS vaccine respectively]) or a single dose of a comparator licensed MMVR vaccine (2 groups of 100 participants each receiving one of the 2 different lots of the MMRV vaccine [MMRV\_Lot 1 and MMRV\_Lot 2], which will be pooled for all analyses). All participants will be required to have been previously primed with a first dose of any combination of measles-, mumps-, rubella- and varicella-containing vaccine(s).

Figure A; Study Schema

Study interventions: MMRV(H)NS, MM(H)RVNS and M(L)M(L)R(L)V(L)NS = investigational vaccine in 3 different formulations; MMRV\_Lot 1 and MMRV\_Lot 2 = comparator vaccine MMRV Lot 1 and Lot 2.

Abbreviations: N = number of participants

Analysis Plan Page 22 of 57

°Before study intervention administration

\*Blood sample for anti-measles, anti-mumps, anti-rubella virus and anti-gE antibody measurements.

#Contact (by telephone call or any other convenient procedure) for the safety follow-up will take place 6 months post-dose of study intervention

Note: Visit 2 (Day 15) for review of post-vaccination safety data may be a virtual visit.

Healthy children aged 4 to 6 years will be enrolled in this study according to the inclusion and exclusion criteria (see protocol Section 5.0). Approximately 800 participants will be randomly assigned to the 5 study interventions in a 2:2:2:1:1 ratio prior to intervention to provide approximately 200 enrolled participants in each MMRVNS group and 100 enrolled participants in each MMRV group (MMRV\_Lot 1 and MMRV\_Lot 2).

Treatments will be allocated using a minimization algorithm for 90% of the participants, with the remaining 10% of treatments allocated randomly. Center and country will be used as minimization factors.

Analysis Plan Page 23 of 57

Table B: Study Groups

Study groups	Number of participants	Age (Min-max)	Study interventions
MMRV(H)NS	200	4 to 6 years	MMRV(H)NS vaccine
MM(H)RVNS	200	4 to 6 years	MM(H)RVNS vaccine
M(L)M(L)R(L)V(L)NS	200	4 to 6 years	M(L)M(L)R(L)V(L)NS vaccine
MMRV_Lot 1	100	4 to 6 years	MMRV vaccine Lot 1
MMRV_Lot 2	100	4 to 6 years	MMRV vaccine Lot 2

The total duration of study participation for an individual participant will be 181 days. There will be 3 study visits: Visit 1 on Day 1, when the participants receive study intervention, Visit 2 on Day 15 (either in-person or virtually, for review of post-vaccination safety data) and Visit 3 on Day 43, when blood sampling for vaccine antibody testing will be performed. A safety call will be made on Day 2 or Day 3 and a safety follow-contact will be made to the participant on Day 181 via telephone or by any other convenient means of communication.

# 3.2. Schedule of Activities

Schedule of events can be found in Section 1.3 of the protocol.

# 3.3. Changes to Analysis from Protocol

The seroresponse thresholds for anti-measles antibodies and anti-rubella antibodies offering clinical benefit were updated and communicated to the FDA. The SAP was updated with the new thresholds but the Protocol was not

Analysis Plan Page 24 of 57

updated.

The assay cut-offs were updated during assay validation for anti-mumps antibodies and anti-rubella antibodies. The SAP was updated but the Protocol was not updated.

The distribution of antibody concentrations for each antigen display using reverse cumulative curves will no longer be for the sub-cohort of initially seronegative participants, due to an expectation of a low number of participants in this sub-cohort.

# 4. PLANNED ANALYSES

The following analyses will be performed for this study:

- Analyses for Independent Data Monitoring Committee (IDMC) meetings
- Analyses for Safety Review Team (SRT) review
- Interim Analysis
- Final Analysis

# 4.1. Independent Data Monitoring Committee (IDMC)

An IDMC SAP, describing the methodology and the presentation of, and access to, results will be provided by IQVIA as a separate document.

An IDMC will provide safety oversight during the active vaccination period, through unblinded review of the cumulative safety data.

The first IDMC review is planned after Day 43 safety follow-up of the first 200 vaccinated participants

Analysis Plan Page 25 of 57

(approximately 50 participants in each group, considering pooled MMRV groups) is completed. The analysis will take place once all 200 participants have returned for their Day 43 visit (Visit 3) within the allowed interval for the visit or have withdrawn from the study. A subsequent IDMC review meeting is planned during the study, after Day 43 safety follow-up of 400 participants is completed.

#### 4.2. SRT Review

The SRT is responsible for ongoing safety monitoring. Monthly SRT reviews will occur up to the enrollment and vaccination of the first 200 participants through their Day 43 follow-up, to monitor cumulative, blinded safety data (including serious and non-serious AEs). The blinded safety data review by the SRT may trigger an emergency adhoc IDMC review before the 200 participants are enrolled and vaccinated.

# 4.3. Interim Analysis

One interim analysis will take place for this study. A statistical analysis including safety and final immunogenicity data for all participants up to Day 43 timepoint is planned, the results of which will be based on the unblinded intervention groups. All analyses are descriptive and therefore no statistical adjustment for interim analyses is required.

# 4.4. Final Analysis

All final, planned analyses identified in this SAP will be performed by IQVIA Biostatistics following Sponsor Authorization of this Statistical Analysis Plan, Database Lock, Sponsor Authorization of Analysis Sets and Unblinding of intervention group.

This SAP is focused/limited to planned interim and final analyses. Outputs required for the interim and final

Analysis Plan Page 26 of 57

analyses will be flagged in the tables, figures and listings (TFL) mock shells document.

# 5. ANALYSIS SETS

Agreement and authorization of participants included/excluded from each analysis set will be conducted prior to the unblinding of the study.

# 5.1. Process for Analysis Set Assignment

- Definitions for analysis sets are provided below.
- Prior to database lock, a transfer of raw data from the electronic Case Report Form (eCRF) will occur, and
  participants will be assigned to analysis sets in accordance with the definitions in this SAP and the available
  data at that time. However, the protocol deviations will be monitored continuously throughout the study.
- Listings presenting participants excluded from each preliminary analysis set and reasons for exclusion will be
  prepared for sponsor review ahead of database lock in order to allow appropriate related data queries to be
  issued.
- Listings presenting participants excluded from each final analysis set and reasons for exclusion will be prepared
  for sponsor review ahead of unblinding for a final review and approval. However, for deviations that can only
  be assessed after unblinding such as vaccination errors these will be reviewed after unblinding.
- A Data Review meeting will be held to confirm analysis set assignment for each participant and any changes
  will be recorded. Changes will be implemented, and an updated analysis set assignment will be approved by the
  sponsor.
- Sponsor authorization of the analysis sets will be necessary to unblind the data after database lock. Once
  approved, the study will be unblinded, analysis sets will be finalized including additional eliminations requiring
  unblinding, and the database will be locked.

Analysis Plan Page 27 of 57

After database lock, the final analysis sets will be derived using the final study data, i.e., clinical database
 (eCRF), external vendor data (immunogenicity results), protocol deviations log and blinded data report.

# 5.2. Enrolled Set [ENR]

All participants who received a study intervention, had a blood draw before study intervention or were randomized.

Note that as per Good Clinical Practice (GCP) enrolled participants' parent(s)/ legally acceptable representative

(LAR) should have completed the informed consent process and participants should be eligible before initiating any study procedure.

# 5.3. Exposed Set [ES]

All participants who received a study intervention. Analysis per group is based on the study intervention administered.

# 5.4. Per Protocol Set [PPS]

All eligible participants who received study intervention as per protocol, were not unblinded, had immunogenicity results pre- and post-dose for at least 1 antigen, complied with blood draw interval between study intervention and post-dose blood sample, without intercurrent medical conditions that may interfere with immunogenicity and without prohibited concomitant medication/vaccination\*.

\*Intercurrent medical conditions that may lead to elimination from the PPS are defined as confirmed immunodeficiency condition, or development of measles, mumps, rubella or varicella illness (chicken-pox) or herpes zoster in the interval between study intervention administration and the collection of the blood specimen for immunogenicity at Visit 3.

Analysis Plan Page 28 of 57

# 6. GENERAL CONSIDERATIONS

Data will be summarized descriptively (frequency and percentage for categorical data and mean, standard deviation [SD] and range for continuous data, unless specified otherwise). In summary tables for categorical data for which categories are defined on the eCRF, all categories will be presented as specified, even if the participant count within that category is zero.

In all the summary tables intervention MMRV lot 1 and MMRV lot 2 will be analyzed as pooled lots.

Unless otherwise specified, all data collected during the trial will be presented in listings for the ENR.

# 6.1. Reference Start Date and Study Day

Study Day will be calculated from the reference start date and will be used to show start/stop day of assessments and events.

Reference start date is defined as the day of the dose of study intervention and will appear in every listing where an assessment date or event date appears.

If the date of the event is on or after the date of study intervention then:

Study Day = (date of event - date of study intervention) + 1.

If the date of the event is prior to the date of study intervention then:

Study Day = (date of event – date of study intervention).

Analysis Plan Page 29 of 57

In the situation where the event date is partial or missing, Study Day, and any corresponding durations will appear as missing in the listings.

#### 6.2. Baseline

Unless otherwise specified, baseline is defined as the last non-missing measurement taken prior to reference start date (including unscheduled assessments). In the case where the last non-missing measurement and the reference start date coincide, that measurement will be considered pre-baseline.

# 6.3. Retests, Unscheduled Visits and Early Termination Data

In general, for by-visit summaries, data recorded at the nominal visit will be presented. Unscheduled measurements will not be included in by-visit summaries.

Listings will include all scheduled, and early termination discontinuation data.

# 6.4. Windowing Conventions

Allowed time window for each visit will be performed as mentioned in "Schedule of Activities", section 1.3 of protocol.

Table C: Intervals between Study Visits

Interval	Planned visit interval	Allowed interval range
Visit 1 → Safety call	1 to 2 days	1 to 3 days
Visit 1 → Visit 2	14 days	14 to 19 days

Analysis Plan Page 30 of 57

Visit 1 → Visit 3	42 days	35 to 56 days
Visit 1→ Safety follow-up contact	180 days	180 to 201 days

#### Table D: Window convention

Assigned Study Day	Visit label as per protocol	Visit assigned
Day 1	Visit 1	Visit 1 (Day 1)
Day 2 to 3 (Day 1 + 1 to 3 days)	Safety Call	Safety Call (Day 2 – 3)
Day 15 (Day 1 + 14 to 19 days)	Visit 2	Visit 2 (Day 15)
Day 43 (Day 1 + 35 to 56 days)	Visit 3	Visit 3 (Day 43)
Day 181 (Day 1 + 180 to 201 days)	Safety Follow-up contact	Safety Follow-up (Day 181)

# 6.5. Statistical Tests

The default significant level will be (5%); confidence intervals will be 95% and all tests will be two-sided, unless otherwise specified in the description of the analyses.

# 6.6. Common Calculations

Geometric Mean Concentration (GMC):

Distributions of antibodies are generally skewed to the right (Nauta, 2010). Therefore, prior to any statistical analysis that assumes normally distributed observations, antibody titers or concentrations will be log10-transformed.

Analysis Plan Page 31 of 57

GMCs and their 95% CI are computed by exponentiating (base 10) the least squares mean and 95% CI of the log10 concentrations.

The GMC will be calculated using the following formula:

$$10^{\left(\frac{\sum_{i=1}^{n}\log 10(t_i)}{n}\right)}$$

Where  $t_1, t_2, ..., t_n$  are n observed immunogenicity concentrations.

Concentration below assay cut-off (i.e., <lower limit of quantification or < LLOQ) will be replaced by half the assay cut-off (LLOQ/2) for the purpose of GMC computation. Concentrations above the upper limit of quantification (ULOQ) will be replaced by the ULOQ value.

Seroresponse rate for measles, mumps and rubella is defined as the percentage of participants for whom the postdose antibody concentration (Day 43), as measured by the anti-measles, -mumps, -rubella Multiplex Luminex based Immuno assay is  $\geq$  to the following threshold values:

- 116 mIU/mL for anti-measles
- 296 AU/mL for anti-mumps
- 24 IU/mL for anti-rubella

Seroresponse rate for varicella is defined as the percentage of participants for whom the post-dose anti-gE antibody concentration (Day 43) is ≥300 mIU/mL.

Analysis Plan Page 32 of 57

#### 6.7. Software Version

All analyses will be conducted using SAS version 9.4.

# 7. STATISTICAL CONSIDERATIONS

# 7.1. Adjustments for Covariates and Factors to be Included in Analyses

The following factors will be used in the analyses: country. For details, refer to section 15.1 and 15.2. The model will include all groups as fixed categorical effects in the Analysis of Variance (ANOVA) model.

For the interim analysis an Analysis of Covariance (ANCOVA) model on log-transformed anti-measles, anti-mumps, anti-rubella and anti-gE with MMRVNS dose level will be used as covariate in addition to the indicator of investigational vaccine. Likewise, seroresponse will be analyzed using a logistic regression with the same covariate. The dose effect will be constrained to be positive.

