9.1 Statistical Hypotheses

There are no statistical hypotheses in this study. All analyses are descriptive.

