9.3.2.2 Between Group Assessments

GMC ratios of pooled MMRV group over each MMRVNS group (MMRV(H)NS, MM(H)RVNS and M(L)M(L)R(L)V(L)NS) will also be provided with nominal 2-sided 95% CI. This will be obtained for each MMRV antigen (i.e., measles, mumps, rubella, and varicella) separately using an analysis of variance model on log-transformed antibody concentrations adjusted for log-transformed pre-dose antibody concentration for the antigen. The country will be added as a covariate. Treatment group will be included in the model and group contrasts with associated 2-sided 95% CI will be exponentiated to obtain treatment group GMC ratios for antibodies against each antigen.

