#### 15.1.3. Primary Analysis of Primary Immunogenicity Variable(s)

The primary immunogenicity endpoints of anti-measles, anti-mumps, anti-rubella and anti-gE antibody GMCs at Day 43 will be summarized by study intervention with their 95% CI derived considering log10-transformed concentrations are normally distributed with unknown variance for antibodies against each antigen. The distribution of antibody concentration for each antigen will be graphically presented by reverse cumulative curves per study intervention. The concentration below the assay cut-off will be assigned to half the cut-off for the purpose of GMC computation. This analysis will be based on the PPS and the ES. The analysis, for PPS only, will also be repeated split by country.

Analysis Plan Page 39 of 57

Table E: Assay cut-off

Component	Assay cut-off	Method
Anti-measles Antibody	29.082 mIU/mL	
immunoglobulin (IgG)		Multiplex Luminex based Immuno Assay
Anti-mumps Antibody IgG	189.240 AU/mL	
Anti-rubella Antibody IgG	1.916 IU/mL	
Anti-gE Antibody IgG	97 mIU/mL	ELISA

Abbreviations: ELISA = Enzyme-linked immunosorbent assay

An adjusted GMC and GMC ratio with 2-sided 95% CI for study intervention which is derived from an ANOVA model on log10 transformed antibody concentration adjusted for log-transformed pre-dose antibody concentration for each antigen. The country will be added as a covariate. Study intervention will be included in the model and group contrasts with associated 2-sided 95% CI will be exponentiated to obtain study intervention GMC ratios for antibodies against each antigen and will be based on the PPS.

The GMC ratio will be estimated along with its corresponding 2-sided 95% CI by exponentiating the least-squares means for the difference.

For the interim analyses, an ANCOVA model on log-transformed anti-measles, anti-mumps, anti-rubella and antigE with MMRVNS dose level will be used as covariate in addition to the indicator of investigational vaccine.

Analysis Plan Page 40 of 57

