#### 15.2.3. Analysis of Secondary Immunogenicity Variables

The percentage of participants with a seroresponse will be summarized by study intervention and corresponding 2-sided 95% exact CI will be reported based on Clopper and Pearson method (Clopper CJ, 1934) for each antigen.

The analysis will also be repeated split by country. These summaries will be produced for PPS and ES.

The number and percentage of participants with a seroresponse at Day 43 for each antigen and 2-sided 95% CI on group difference in the seroresponse rate (MMRV pooled group – MMRVNS group [different potencies])- will be computed based on Miettinen and Nurminen method (Miettinen O., 1985) for PPS.

For interim analyses, seroresponse for each antibody will be analyzed using a logistic regression with MMRVNS potencies used as a covariate for PPS. The dose effect will be constrained to be positive.

Analysis Plan Page 41 of 57

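### The interim dose-level models force a non-negative dose effect with no unconstrained estimate beside it, and SAP 7.1 and 15.1.3 disagree on whether this covers the ANCOVA (minor)

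*SAP*

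**What the plan says.** - **SAP 7.1** describes the interim ANCOVA, then a logistic regression for seroresponse with the same covariate, and closes the paragraph with "The dose effect will be constrained to be positive". Its position after both models suggests that it applies to both.
- **SAP 15.1.3** restates the interim ANCOVA "with MMRVNS dose level will be used as covariate in addition to the indicator of investigational vaccine". The constraint is not mentioned. Pre-dose concentration is not named either, although the main GMC-ratio model just above is "adjusted for log-transformed pre-dose antibody concentration for each antigen" and includes country.
- **SAP 15.2.3**: "For interim analyses, seroresponse for each antibody will be analyzed using a logistic regression with MMRVNS potencies used as a covariate for PPS". The constraint is repeated directly after this sentence.
- **SAP 4.3**: the interim analysis covers "safety and final immunogenicity data for all participants up to Day 43 timepoint".
- **Protocol 9.3.2.2** names "GMC ratios of pooled MMRV group over each MMRVNS group" as the between-group summary for concentrations. SAP 15.2.3 likewise sets pooled MMRV against the MMRVNS groups for seroresponse differences.
- **Protocol 9.1**: "There are no statistical hypotheses in this study. All analyses are descriptive". Protocol Section 9 does not describe the dose model.

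Neither document gives a reason for the constraint, a numeric dose coding, an interval method for the constrained coefficient, or an unconstrained version of the dose fit. Country is listed in SAP 7.1 as a factor for the analyses but is not named in the interim ANCOVA sentence.

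**The concern.** The three MMRVNS formulations differ in potency by design, and the dose-level models are where the SAP describes how response changes with potency. Fixing the sign in advance assumes the direction of the relationship that the model is there to describe. If response were flat or fell with potency, the fit would return a slope at or above zero, and nothing in the dose-model output would tell the reader that the data pointed the other way. Because the interim uses final Day 43 immunogenicity data and no later dose fit is planned, this would be the dose model of record.

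The mismatch between 7.1 and 15.1.3 is a separate, practical problem: two programmers could fit different ANCOVAs from the same SAP.

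A smaller point is that the interim ANCOVA does not name the pre-dose concentration. Leaving it out of a linear model in a randomised comparison costs precision only.

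**Working it through.** **Inputs.** From Protocol 9.5: 160 evaluable per MMRVNS group, 160 in pooled MMRV (2 x 80), and 0.45 on the log10 scale. From the Protocol synopsis, the levels per antigen: measles and rubella have two (low; release in two arms), mumps and varicella have three (low, release, high). The numeric potencies for the covariate are not given, so I assume codings scaled 0 to 1: (0,1,1) for two levels and (0,0.5,1) for three. The MMRVNS arms alone are taken to determine the slope. Positive is read as not below zero.

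**The plan's own figure.** 10^(1.96 x 0.45 x sqrt(2/160)) = 10^0.0986 = 1.255-fold, against the stated 1.25. So 0.45, though called a standard error, works as a per-participant SD.

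**SE of the lowest-to-highest dose effect.** SE = 0.45 / sqrt(160 x SSx), where SSx is the sum of squared deviations of the three codes.
- (0,1,1): SSx = 0.667, SE = 0.0436.
- (0,0.5,1): SSx = 0.500, SE = 0.0503.

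Unequal spacing, (0,0.25,1) or (0,0.75,1), gives 0.0483, inside this range.

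**Concentrations (only if the constraint covers the ANCOVA).** With unconstrained estimate b ~ N(d, SE), the constrained estimate is max(0, b). P(zero) = Phi(-d/SE), its mean is d x Phi(d/SE) + SE x phi(d/SE), and P(unconstrained 95% CI wholly below zero) = Phi(-1.96 - d/SE).

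| True effect d (log10) | Constrained slope zero | Unconstrained CI wholly below 0 |
|---|---|---|
| 0 | 50% | 2.5% |
| -0.05 (0.89-fold) | 84-87% | 17-21% |
| -0.10 (0.79-fold) | 98-99% | 51-63% |

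At d = 0 the mean is biased upward by 1.041- to 1.047-fold, which is small beside the planned 1.25-fold half-width. At d = +0.05 the bias is 1.006- to 1.010-fold. At d = -0.10 the bias in the fitted log10 mean at dose x is (E[max(0,b)] - d) x (x - mean x). The fitted GMC is then 0.86-0.89 times its true value at the lowest dose and 1.08-1.12 times at the highest.

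**Seroresponse (the constraint is explicit in both 7.1 and 15.2.3).** The constrained logistic slope is zero when the score, sum of x(y - mean y), is not above zero. Simulated response rates are assumptions; 2,000,000 trials each.

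| True rates | Coding | Score below 0 | Tie | Slope zero |
|---|---|---|---|---|
| 97% in all arms | (0,1,1) | 47.4% | 7.5% | 55% |
| 97% in all arms | (0,0.5,1) | 43.3% | 13.3% | 57% |
| Low 98%, release 97% | (0,1,1) | 72.5% | 6.5% | 79% |
| Low 99%, release 96% | (0,1,1) | 98.2% | 0.8% | 99% |

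In a tie the unconstrained slope is zero too, so ties are not an effect of the constraint.

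**Would an unconstrained logistic fit exist?** With two levels the slope diverges when the low arm has no non-responders: 0.99^160 = 0.20 at a true 99%. With three levels it is normally finite: 0, 6 and 6 non-responders of 160 at x = 0, 0.5 and 1 give a slope of -1.71 (SE 0.84). At 99%, 96% and 96%, divergence in this direction occurs in about 0.03% of trials.

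**Pre-dose concentration.** With pre/post correlation r (none is given; 0.3, 0.5 and 0.7 assumed), including it multiplies the SE by sqrt(1 - r^2), a reduction of 5%, 13% or 29% if 0.45 is an unadjusted SD. If 0.45 is already adjusted, leaving it out raises the SE by 5%, 15% or 40%.

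**The case against.** The strongest reply is that an order restriction is an ordinary, pre-specified and disclosed modelling choice. It assumes that response does not fall with potency, and nothing in the documents suggests that it does. The restriction also helps when the effect is small: at zero effect the RMSE is 0.031 against 0.044 unconstrained for two levels, and 0.036 against 0.050 for three. That stands, and is why the constrained fit need not be removed.

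Second, a reader might infer that these are the SAP's only models of response across potency, and that a reversal would go unseen. The documents do not support that. The main ANOVA enters all groups as categorical effects, adjusts for pre-dose concentration and country, and gives adjusted GMCs by formulation. For measles and rubella, low against release is a simple contrast in that model. By-group GMCs and Clopper-Pearson intervals would also show the ordering.

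Third, a reader might infer that no unconstrained interval between formulations is planned at all. That is too firm. The ratios and differences explicitly named with intervals are against pooled MMRV, but 15.1.3 also promises group contrasts with 95% CIs and does not expressly limit them to comparisons with MMRV. Output content is deferred to mock shells, which are not among the documents.

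Fourth, reading the interim ANCOVA as dropping pre-dose concentration or country is an inference from silence. That is fair: what is needed is confirmation, and the cost of omission is precision only.

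What remains is narrow: no unconstrained dose coefficient is planned, and two SAP sections disagree on the scope of the constraint.

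**Conclusion.** The point holds as a minor one. As written, the interim dose model cannot show a falling response, and for the ANCOVA it is unclear whether the constraint applies at all. Under the assumptions above, a true reversal of -0.10 log10 would appear as no dose effect in 98-99% of trials, whereas an unconstrained 95% CI would lie wholly below zero in 51-63%. For seroresponse, where the constraint is explicit, the slope is zero in 55-57% of trials with equal 97% rates, and in 79-99% under the two reversals tried. The sizes depend on the assumed codings and response rates; the direction does not.

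It would be wrong to conclude that the primary results are biased. By-group GMCs, reverse cumulative curves, the categorical ANOVA with its GMC ratios, and seroresponse rates and differences do not use the constrained slope. No hypothesis, estimand or decision rule depends on the dose models, and with no true effect the upward bias on concentrations is only 1.04- to 1.05-fold.

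**What to change.** **(a) SAP 7.1, 15.1.3 and 15.2.3.** Keep the constrained fit if it is wanted, labelled as such, and report beside it the unconstrained dose coefficient with its 2-sided 95% CI. Make 7.1 and 15.1.3 agree on whether the constraint applies to the ANCOVA. State the numeric dose coding for each antigen. For the two-level antigens only (measles, rubella), specify a penalised or profile-likelihood logistic fit for the case where the low arm has no non-responders. Mumps and varicella, with three levels, do not normally need this.

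**(b) SAP 7.1 and 15.1.3.** State that log10 pre-dose concentration is a covariate in the interim ANCOVA, as in the main GMC-ratio model, and confirm whether country is included.

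**Cost.** SAP wording and a few lines of code; the Day 1 samples are already scheduled. The downside is that the unconstrained slope is more variable near zero effect (the RMSE figures above) and may be negative, which the text around the output should be ready to explain.
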